### **9.2.3 Suspected unexpected serious adverse reactions (SUSARs)**

Adverse reactions are all untoward and unintended responses to an investigational product related to any dose administered.

Unexpected adverse reactions are SUSARs if the following three conditions are met:

1. the event must be serious (see chapter 9.2.2);
2. there must be a certain degree of probability that the event is a harmful and an undesirable reaction to the medicinal product under investigation, regardless of the administered dose;
3. the adverse reaction must be unexpected, that is to say, the nature and severity of the adverse reaction are not in agreement with the product information as recorded in:
  - Summary of Product Characteristics (SmPC) for an authorised medicinal product.

All SUSARS occurring between randomisation and the end of follow-up at day 90 ( $\pm$  14 days) have to be reported by the local Investigator to the study Sponsor within 24 hours of Investigator's first awareness about the event. The sponsor will report the following SUSARs through the web portal *ToetsingOnline* to the METC in an expedited fashion:

- SUSARs that have arisen in the clinical trial that was assessed by the METC;
- SUSARs that have arisen in other clinical trials of the same sponsor and with the same medicinal product, and that could have consequences for the safety of the subjects involved in the clinical trial that was assessed by the METC.

The remaining SUSARs are recorded in an overview list (line listing) that will be submitted once every half year to the METC. This line listing provides an overview of all SUSARs from the study medicine, accompanied by a brief report highlighting the main points of concern. The expedited reporting of SUSARs through the web portal Eudravigilance or *ToetsingOnline* is sufficient as notification to the competent authority.

In the event this becomes applicable, the Sponsor will report all SUSARs to the competent authorities in other Member States in an expedited fashion, according to the requirements of the Member States.

The expedited reporting will occur not later than 15 days after the sponsor has first knowledge of the adverse reactions. For fatal or life threatening cases the term will be maximal 7 days for a preliminary report with another 8 days for completion of the report.

### 9.3 Annual safety report

In addition to the expedited reporting of SUSARs, the sponsor will submit, once a year throughout the clinical trial, a safety report to the accredited METC, competent authority, and (in the event this becomes applicable) competent authorities of the concerned Member States.

This safety report consists of:

- a list of all suspected (unexpected or expected) serious adverse reactions, along with an aggregated summary table of all reported serious adverse reactions in the present study, ordered by organ system;
- a report concerning the safety of the subjects, consisting of a complete safety analysis and an evaluation of the balance between the efficacy and the harmfulness of the medicine under investigation.

### 9.4 Follow-up of adverse events

All SAEs occurring between randomisation and day 7, and all SUSARs occurring between randomisation and the end of follow-up at day 90 ( $\pm$  14 days) will be followed until they have abated, or until a stable situation has been reached. Depending on the event, follow up may require additional tests or medical procedures as indicated, and/or referral to the general physician or a medical specialist.

SAEs need to be reported till end of study within the Netherlands, as defined in the protocol.

### 9.5 Data Safety Monitoring Board (DSMB)

An independent Data and Safety Monitoring Board (DSMB) will oversee the safety of patients in the trial and the efficacy of the intervention under study. They will work in accordance with a dedicated charter and will follow processes recommended by the DAMOCLES statement. The DSMB will meet in person or by telephone at least annually. With respect to safety, the DSMB will conduct unblinded interim analyses after every 100 patients have completed follow-up, until at least patient number 1000. With respect to efficacy, the DSMB will conduct unblinded interim analyses after 900 patients had their final follow-up. DSMB members will receive listings of all SAE reports as well as unblinded aggregate summaries of data by treatment group for review in closed meetings. Feedback, blind to treatment, will be provided in open meetings and in written conclusions to the sponsor and the MR ASAP project leaders.

## 10. STATISTICAL ANALYSIS

### 10.1 Statistical analysis plan (SAP)

The analysis and reporting of the trial will be in accordance with CONSORT guidelines. Before follow-up will have been completed, a statistical analysis plan (SAP) will be developed that will specify: (i) Hypotheses to be tested; (ii) Treatment effects to be estimated in order to satisfy the primary and secondary objectives of this trial; (iii) Technical description of the statistical methodology and procedures for performing the statistical analysis of outcome measures and SAE data; (iv) Primary, secondary, and sensitivity analyses; and (v) Subgroup analyses. The SAP will be signed off by the trial Executive Committee and then uploaded on the public area of the trial website. The final statistical analysis will be performed once recruitment has ceased, final follow-up has been completed, final data have been checked and any errors corrected, and the database has been locked.

All analyses will be performed according to the intention-to-treat principle. Baseline data by treatment allocation will be reported with statistical procedures. Missing values for baseline characteristics will be reported. Missing baseline characteristics will be imputed using regression imputation.

### 10.2 Primary outcome

The primary effect estimate will be a shift in the mRS score at 90 days ( $\pm$  14 days) assessed by means of ordinal logistic regression, and will be expressed as a common odds ratio with 95% confidence interval. The assumption of proportional odds will be assessed using the likelihood ratio test. The statistical analyses will be performed according to the intention-to-treat principle and adjusted for relevant baseline characteristics including age, sex, stroke type, score on the FAST at study inclusion, time of symptom onset to randomisation, pre-stroke score on the mRS, and ambulance region.

### 10.3 Secondary outcomes

Binary logistic regression will be used for binary outcomes, including death, unfavourable outcome, and SAEs. Ordinal logistic regression will be used for ordered categorical data and multiple regression will for continuous outcomes. Wilcoxon rank sum test will be used for continuous outcome measures which are not normally distributed.

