#### 4.4 Sample size calculation

MR ASAP is powered to detect a statistically significant shift in the distribution of the scores on the mRS at 90 days in the overall study population, assuming an effect that leads to a 7% absolute risk reduction (ARR) for poor functional outcome (mRS 3 - 6) in the GTN group compared with controls (48% vs 41%). The risk of a poor functional outcome of 48% is based on findings in the Field Administration of Stroke Therapy – Magnesium (FAST-MAG) trial, a trial including 1700 patients with suspected stroke in the prehospital setting. This effect is considerably smaller than the 23% ARR observed in the small phase II trial RIGHT, with patients treated within 4 hours of stroke onset, and smaller than the 9% ARR in the subgroup of patients enrolled in ENOS within 6 hours of symptom onset. We consider a 7% ARR sufficient to change clinical practice. We assume that the use of covariate adjustment will increase statistical efficiency by 20%, which is based on the R^2 in the MR CLEAN trial data of an adjustment model containing age, pre-stroke mRS and items 4, 5a, 5b, 9 and 10 of the NIHSS that correspond to the FAST score. The sample size calculations are based on a simulation study with a proportional odds model. A total study size of 1280 patients then allows for a power of 80% to detect a difference at a 5% significance level in the scores on the mRS in patients treated with GTN as compared with controls. As we expect to include around 10% stroke mimics, in whom no treatment benefit is expected we increase this sample size with 10% and aim for inclusion of 1400 patients.

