##### At 90 days ( $\pm 14$ days):

- Death;
- Dichotomized mRS of 0-1 vs. 2-6;
- Dichotomized mRS of 0-2 vs. 3-6;
- Dichotomized mRS of 0-3 vs. 4-6;
- Disability assessed with the score on the Barthel Index (BI);
- Quality of life assessed with the EuroQol 5D-5L (EQ-5D-5L);

- Home time: the number of nights among the first 90 days since stroke onset that are spent in the patient's own home or a relative's home. Where final follow-up occurs earlier, the last known placement will be extrapolated to 90 days;
- Patient location over first 90 days ( $\pm$  14 days): hospital; rehabilitation service; chronic nursing facility; home.

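### Section 10.3 assigns skewed continuous secondary outcomes to an unadjusted Wilcoxon test, although a covariate-adjusted model would cost nothing and could be more precise (minor)

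*Protocol*

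**What the plan says.** Section 10.3 assigns a method to each type of secondary outcome: binary logistic regression for binary outcomes, ordinal logistic regression for ordered categories, and "multiple regression will for continuous outcomes" (a verb is missing). It then makes one exception: "Wilcoxon rank sum test will be used for continuous outcome measures which are not normally distributed". It names no covariates for any of these analyses and does not list which outcomes fall under which rule.

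Covariates appear in section 10.2, for the primary outcome only, where the ordinal model is "adjusted for relevant baseline characteristics including age, sex, stroke type, score on the FAST at study inclusion", together with time from onset to randomisation, pre-stroke mRS and ambulance region. Section 4.4 gives the reason for adjusting: "We assume that the use of covariate adjustment will increase statistical efficiency by 20"%. That figure comes from another trial's data, with an "adjustment model containing age, pre-stroke mRS and items 4, 5a, 5b, 9 and 10 of the NIHSS".

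The outcomes that the exception could reach are in section 8.1.2. The clearest is "Home time: the number of nights among the first 90 days since stroke onset" spent at the patient's own or a relative's home. The others are the perfusion-deficit volume and the haemorrhage volume on admission.

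**The concern.** A two-sample rank sum test compares the arms and takes no covariates. For the outcomes sent to it, prognostic variables that the trial records anyway, such as age, pre-stroke mRS and FAST score, go unused. If they predict the outcome, precision is lost. The test itself gives a p-value; any shift estimate that accompanies it is unadjusted.

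The rule also depends on what the data look like. Home time could be reported as a mean difference from a regression or as a rank comparison, depending on how its distribution is judged at the end. These are different quantities, and for bounded or skewed outcomes the choice can be made now.

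The outcomes are not marginal. The protocol summary names home time and quality of life among its three example secondary outcomes, and section 2 makes the effect on ischaemic core and salvageable tissue a secondary objective.

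**Working it through.** **1. Which outcomes does the exception reach?** Taking the protocol's own labels:

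| Outcome | How the protocol describes it | Method under 10.3 |
|---|---|---|
| Home time (8.1.2, 8.3.12) | count of nights, 0 to 90 | Wilcoxon if judged non-normal, which is likely |
| Perfusion-deficit or haemorrhage volume (8.1.2) | volume | Wilcoxon if judged non-normal, which is likely |
| EQ-5D-5L (8.3.11, Appendix 7) | five items with five levels; no index defined | Wilcoxon only if an index value is derived and is non-normal |
| Barthel Index (8.3.10, Appendix 6) | ordinal scale | ordinal regression |
| NIHSS (8.3.4, Appendix 4) | ordinal scale | ordinal regression |
| Blood pressure, pulse, temperature (8.1.2) | continuous | multiple regression |

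The point therefore concerns home time, the volumes and possibly an EQ-5D-5L index.

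**2. What is the 20% attached to?** The inputs in section 4.4 are a "7% absolute risk reduction (ARR) for poor functional outcome (mRS 3 - 6) in the GTN group compared with controls (48% vs 41"%), and "A total study size of 1280 patients then allows for a power of 80% to detect a difference at a 5% significance level". A check on the dichotomised outcome, two-sided and 1:1 (both assumed), with pooled variance under the null:

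- n per arm = [1.960 × √(2 × 0.445 × 0.555) + 0.842 × √(0.48 × 0.52 + 0.41 × 0.59)]² / 0.07² = 790.04, rounded up to 791, or 1582 in total.
- 1582 × 0.80 = 1266, within 3% of 1280. Reading the gain as a divisor, 1582 / 1.2 = 1318, also within 3%.

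The protocol says it simulated a proportional odds model but gives no mRS distribution, so its run cannot be repeated. Whitehead's formula with four assumed distributions (48% at mRS 3–6) gives 1198 to 1205 unadjusted and 958 to 964 after a 20% reduction. Nothing below depends on this. What matters is that the 20% enters the mRS calculation and nothing else.

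**3. What could the loss be?** No effect size, standard deviation or R² is given for any continuous secondary outcome, so a range has to be assumed. If covariates explain a share R² of the variance, the unadjusted analysis has (1 − R²) times the information of the adjusted one. Starting from 80% adjusted power (1.960 + 0.842 = 2.802):

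unadjusted power = Φ(2.802 × √(1 − R²) − 1.960)

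| R² (assumed) | Unadjusted power | Sample size ratio 1/(1 − R²) |
|---|---|---|
| 0 | 80.0% | 1.00 |
| 0.05 | 78.0% | 1.05 |
| 0.10 | 75.7% | 1.11 |
| 0.20 | 70.7% | 1.25 |
| 0.25 | 67.9% | 1.33 |

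**4. Does this hold for a bounded outcome?** A simulation used a normal latent variable scaled, rounded and cut to 0–90, with 1280 patients, an assumed shift of 0.157 latent standard deviations, one baseline covariate and 3000 runs per setting. It compared the Wilcoxon test with covariate-adjusted linear regression on ranks:

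| Latent R² (assumed) | Wilcoxon | Adjusted rank regression |
|---|---|---|
| 0 | 74.9% | 74.6% |
| 0.1 | 74.9% | 79.2% |
| 0.2 | 76.4% | 83.6% |
| 0.3 | 75.3% | 86.4% |

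The simulation error is about 0.8 points per entry (√(0.75 × 0.25 / 3000) = 0.0079). With a covariate of no prognostic value the two agree within that error. Otherwise the adjusted analysis has more power.

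**The case against.** The rank sum test is valid in a randomised comparison, no bias is shown, and no secondary outcome is powered. Section 10.1 leaves the treatment effects to be estimated and the technical methods to the SAP, which is not shown. It may add a Hodges–Lehmann shift with an interval, a criterion for non-normality and a list of outcomes. A distribution check could also be made on pooled data, since section 8.2 keeps allocation apart from the main database. All of this stands, so the absence of those details is not a finding. It does not remove the point: an SAP that follows the Wilcoxon sentence would still analyse home time and volumes without adjustment.

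A reader might infer three stronger things that the protocol does not support:

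- **That these outcomes forfeit the 20% gain of section 4.4.** That gain was assumed for the mRS, with NIHSS items in place of FAST and without sex, stroke type, onset time or region. It belongs neither to these outcomes nor exactly to the covariates of 10.2.
- **That most quantitative secondary outcomes are affected.** The Barthel Index and NIHSS are labelled ordinal, and vital signs can stay in multiple regression.
- **That 10.3 contradicts a stated plan to adjust secondary outcomes.** It contains no such statement; the intention is only inferred from its choice of regression models.

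It is also fair to say that a common odds ratio for home time is not on a common footing with one for the mRS, and is harder to read than nights.

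**Conclusion.** The point holds in a limited form. Section 10.3 fixes a method that cannot adjust, yields no adjusted effect estimate and is selected from the observed distribution, for a small group of outcomes that includes home time and lesion volumes. It is valid but less precise wherever the baseline covariates are prognostic.

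The loss cannot be fixed from the protocol. On an assumed 0 to 25% of variance explained, 80% adjusted power corresponds to about 80% to 68% unadjusted, and the range includes no loss at all. The 80% starting point is itself hypothetical. Power and type I error for the primary outcome are unaffected. This is a cheap, minor improvement.

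**What to change.** Replace the Wilcoxon sentence in 10.3 with text along these lines, and carry it into the SAP before allocation is unblinded:

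> Home time, haemorrhage and perfusion-deficit volumes and any derived EQ-5D-5L index value will be analysed by cumulative-logit regression on the outcome values, adjusted for the section 10.2 covariates where applicable, and reported as an adjusted common odds ratio with 95% confidence interval, with medians by arm. The Wilcoxon rank sum test will be a sensitivity analysis.

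Where applicable needs two clarifications. Stroke type drops out for intracerebral haemorrhage volume, where it is constant. Small imaging subsets should carry few or no ambulance region terms, as there may be up to 10 regions. The Barthel Index stays under ordinal regression, as 10.3 already implies. Another prespecified adjusted model, such as regression after a transformation, would also serve.

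The cost is one sentence and no new data. The downsides are reliance on proportional odds, which the primary analysis already uses, and an odds ratio that is less directly readable than nights or millilitres; hence the medians.

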#### 10.4 Subgroup analyses

Comparison of the primary outcome in the intervention group vs. control will be performed in the following pre-specified subgroups:

- Age ( $\leq 70$ ,  $> 70$  years);
- Sex (male, female);
- Stroke type (ischaemic stroke, intracerebral haemorrhage);
- In patients with ischaemic stroke: visible occlusion of the proximal intracranial arteries (internal carotid artery (ICA); basilar artery (BA); first or second segment middle cerebral artery (MCA), anterior cerebral artery (ACA), or posterior cerebral artery (PCA));
- Intravenous thrombolysis (yes; no);
- Intra-arterial treatment (yes; no);
- Blood pressure, dichotomised at the median;
- Stroke severity at presentation in the hospital;
- Time to treatment ( $< 90$  minutes;  $\geq 90$  minutes).

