The phase III randomised Rapid Intervention With Glyceryl Trinitrate in Hypertensive Stroke Trial-2 (RIGHT-2) was based on the promising findings in the studies above. RIGHT-2 randomised 1149 adults with presumed stroke within 4 hours of onset who had a face-arm-speech test score of 2 or 3 and systolic blood pressure of 120 mm Hg or higher to transdermal GTN (5 mg once daily for 4 days) or a similar sham dressing. Treatment was started in the ambulance by paramedics, with treatment continued in hospital. The median time to randomisation was 71 min (IQR, 45 to 116). 597 (52%) patients had ischaemic stroke, 145 (13%) had intracerebral haemorrhage, 109 (9%) had transient ischaemic attack, and 297 (26%) had a non-stroke mimic at the final diagnosis of the index event. In the GTN group, participants' systolic blood pressure was lowered by 5.8 mm Hg compared with the sham group ( $p < 0.0001$ ), and diastolic blood pressure was lowered by 2.6 mm Hg ( $p = 0.0026$ ) at hospital admission. Early administration of GTN did not have an effect on functional outcome in patients with a final diagnosis of stroke or transient ischaemic stroke (adjusted common odds ratio for poor outcome (acOR), 1.25; 95% CI, 0.97 to 1.60;  $p = 0.083$ ), nor in the complete population (acOR, 1.04; 95% CI, 0.84 to 1.29;  $p = 0.69$ ). There was also no

difference in the risk of death at 90 days (19% vs 17%; acOR, 1.11; 95% CI, 0.84 to 1.47;  $p = 0.47$ ) or in the risk of serious adverse events. Remarkably, GTN was associated with an improved functional outcome in patients with a stroke mimic (acOR, 0.54; 95% CI, 0.34 to 0.85;  $p=0.0081$ ). This positive finding was not localised to any particular type of mimic. In subgroup analysis, a tendency towards harm of GTN in RIGHT-2 was seen in patients with intracerebral haemorrhage, very early stroke (<1 h), and severe stroke. Furthermore, patients with intracerebral haemorrhage treated with GTN had larger haematoma size and more mass effect on hospital admission.

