### ***Secondary objectives***

To assess whether the effects of transdermal GTN, started within 3 hours of symptom onset in the prehospital setting, on functional outcome at 90 days are consistent across specific subgroups of patients, i.e., those with 1. ischaemic stroke; 2. ischaemic stroke treated with endovascular techniques; or 3. intracerebral haemorrhage.

To assess the effect of GTN on collaterals, size of the ischemic core and salvageable brain tissue on admission to the hospital.

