### 5.2 Use of co-intervention

Patients in each study group will be treated according to national and international guidelines and local protocols of ischaemic stroke, intracerebral haemorrhage, or any other condition that may be diagnosed. Participation in this study is NOT a contra-indication to e.g., intravenous thrombolysis or intra-arterial treatment for ischaemic stroke or surgical treatment for intracerebral haemorrhage. Participation in this study does also not preclude inclusion in a subsequent intervention study, as long as this is not directed at blood pressure modification (see explanatory flowchart and text in Appendix 2).

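### The intra-arterial treatment subgroup in section 10.4 is not restricted to ischaemic stroke as the secondary objective is, so its untreated stratum mixes diagnoses

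*Protocol*

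**What the plan says.** Protocol section 2 (Secondary objectives) asks whether the effect on functional outcome is consistent across named subgroups, "i.e., those with 1. ischaemic stroke; 2. ischaemic stroke treated with endovascular techniques; or 3. intracerebral haemorrhage". The second of these is defined within ischaemic stroke.

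Section 10.4 plans a comparison of GTN with control within pre-specified subgroups. One bullet is "Intra-arterial treatment (yes; no"; intravenous thrombolysis is listed in the same form. Neither names a diagnosis. Another bullet in the list does: "In patients with ischaemic stroke: visible occlusion of the proximal intracranial arteries".

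The analysis population is set in 10.1: "All analyses will be performed according to the intention-to-treat principle". Mimics are part of it. Section 4.4 reads "As we expect to include around 10% stroke mimics, in whom no treatment benefit is expected" and raises the sample size to 1400 for that reason. Section 5.1 has the patch removed in patients who prove to have neither TIA nor stroke, but does not drop them from analysis. Section 5.2 describes who can receive the procedure: "intra-arterial treatment for ischaemic stroke or surgical treatment for intracerebral haemorrhage".

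**The concern.** The list states a restriction to ischaemic stroke where one is meant, and the two treatment bullets lack it. Followed as written, everyone treated intra-arterially has, in effect, ischaemic stroke. Everyone not treated is a pool of untreated ischaemic stroke, haemorrhage, TIA and mimics.

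That matters only if the GTN effect differs by diagnosis, and the protocol gives reasons to expect this. Section 4.4 assumes no benefit in mimics. Section 13.1(i) says that effects in RIGHT-2 appeared to depend on final diagnosis. Section 1.8 reports a tendency to harm in haemorrhage and "improved functional outcome in patients with a stroke mimic (acOR, 0.54; 95% CI, 0.34 to 0.85". Adjusting for stroke type as a main effect (10.2) removes prognostic differences between diagnoses, but not a treatment effect that varies between them.

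Sections 1.10 and 13.2 rest part of the case for the trial after RIGHT-2 on higher Dutch endovascular rates. A reader may therefore set the two strata side by side, and case mix alone could then suggest effect modification by endovascular treatment, or hide it.

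**Working it through.** The protocol gives no figure for this contrast and no endovascular rate, so the rate *f* among ischaemic strokes is assumed and varied.

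**Inputs from the protocol**
- Design effect (4.4): 48% against 41% poor outcome, so OR = (0.41/0.59)/(0.48/0.52) = 0.753.
- Mimics (4.4): 10%, no benefit (OR 1.0).
- Ischaemic to haemorrhagic stroke (1.1): 80:15.
- RIGHT-2 diagnoses (1.8): 597 ischaemic, 145 haemorrhage, 109 TIA, 297 mimic; total 1148.
- RIGHT-2 effects (1.8): 1.25 in stroke or TIA, 0.54 in mimics.

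**Step 1. Other diagnoses in the untreated stratum**

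Share = (all − ischaemic) / (all − *f* × ischaemic)

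- Protocol mix (10% mimics; the other 90% split 80:15; TIA set to 0): ischaemic 0.9 × 80/95 = 0.758. At *f* = 0.10, 0.242/0.924 = 26%. At *f* = 0.40, 0.242/0.697 = 35%.
- RIGHT-2 mix: at *f* = 0.10, 551/1088.3 = 51%. At *f* = 0.40, 551/909.2 = 61%.

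TIA is counted in the RIGHT-2 shares, but the steps below give it the same effect as ischaemic stroke, so it adds no distortion.

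**Step 2. Distortion when endovascular treatment modifies nothing**

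The log odds ratio in the untreated stratum is approximated by the share-weighted mean of the log odds ratios by diagnosis. The correct ratio of odds ratios (treated over untreated) is 1.00.

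*Protocol's own assumptions (0.753 in stroke, 1.0 in mimics).* With *m* the mimic share of the untreated stratum, the untreated OR is 0.753^(1−m) and the ratio is 0.753^m.
- Protocol mix: *m* = 0.108 to 0.144, untreated OR about 0.78, ratio 0.97 to 0.96.
- RIGHT-2 mix: *m* = 0.273 to 0.327, untreated OR 0.81 to 0.83, ratio 0.93 to 0.91.

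*RIGHT-2 effects taken as real,* with *f* = 0.15–0.30. The ratio is (1.25/0.54)^m.
- RIGHT-2 stroke types rescaled to 10% mimics: *m* = 0.110 to 0.123, ratio 1.10 to 1.11.
- 26% mimics: *m* = 0.281 to 0.307, ratio 1.27 to 1.29.
- Proportional odds fits to mixtures of assumed mRS distributions give slightly less: 1.09–1.10 and 1.25–1.27.

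*Haemorrhage OR assumed to be 1.5* (not in the protocol), 0.753 in ischaemic stroke and TIA, 1.0 in mimics: about 0.83–0.87 over the same rates and mimic shares.

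The distortion can go either way.

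**Step 3. Size against sampling error**

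For N patients in equal arms on the seven-level mRS, var(log OR) ≈ 12/(0.97 N). With the RIGHT-2 stroke types rescaled to 10% mimics and *f* = 0.15 to 0.30, there are 133 to 265 treated and 1267 to 1135 untreated patients among 1400.
- SE of the log ratio = √[(12/0.97)(1/133 + 1/1267)] = 0.32, falling to √[(12/0.97)(1/265 + 1/1135)] = 0.24.
- The 95% interval therefore spans a factor of about 1.6 to 1.9 each way.
- A ratio of 0.96 is |ln 0.96| = 0.04, under 0.2 SE. A ratio of 0.83 is |ln 0.83| = 0.19, under 1 SE.

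**Step 4. After restriction to ischaemic stroke**

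Other diagnoses in the untreated stratum fall to 0%. The comparison group becomes 751 to 619 patients, and the SE becomes √[(12/0.97)(1/133 + 1/751)] = 0.33 to √[(12/0.97)(1/265 + 1/619)] = 0.26.

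**The case against.** A reader might infer that the planned consistency test is itself confounded by diagnosis. The text does not support that. The objective names no untreated group. Its three subgroups are all delivered: ischaemic stroke and haemorrhage through the stroke-type bullet, and endovascularly treated ischaemic stroke through the treated stratum. Section 10.4 specifies GTN against control within each subgroup and states no interaction test. Appendix 2 mentions interaction tests only in connection with co-enrolment in the other consortium trials. This part of the objection stands: the fault lies in the comparison stratum, not in the estimate that the objective names.

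It also stands that the effect is small on the protocol's own assumptions, and that the larger figures depend on treating RIGHT-2 subgroup findings as true effects. Sections 1.8 and 13.2 themselves allow that these may be chance.

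It can further be said that subgroup denominators belong in the SAP. Section 10.1 does leave subgroup detail to it. But 10.4 calls its subgroups pre-specified and restricts one bullet while leaving its neighbours open, so the protocol has already worded the split in a way that does not match its objective.

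Lastly, restriction does not isolate effect modification. Intra-arterial treatment generally follows randomisation in the ambulance (8.1.2 lists it among the 24-hour outcomes), and within ischaemic stroke it still tends to separate proximal occlusion from the rest. That is correct and limits what the fix can claim.

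**Conclusion.** The mismatch between the objective and 10.4 is real, and so is the mixing of diagnoses in the untreated stratum. Its consequence is modest: a ratio of odds ratios of 0.96–0.97 where 1.00 is correct on the protocol's assumptions, or 0.91–0.93 with the RIGHT-2 case mix. These rest on an assumed endovascular rate of 10–40% and a log-average approximation. Values of 0.83–0.87 or 1.09–1.27 are conditional on effects that the protocol does not establish. It would go too far to say that a false difference will appear: at the 10% mimic rate, the distortions calculated here lie within one standard error of the contrast. This is a cheap improvement to a secondary analysis, worth making because the comparison should match the objective. The primary analysis is not touched.

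**What to change.** In 10.4, give both treatment bullets the restriction that the occlusion bullet already has: *In patients with ischaemic stroke: intravenous thrombolysis (yes; no); intra-arterial treatment (yes; no)*. Make any comparison of treated with untreated strata within ischaemic stroke only. Add a sentence that treatment is generally decided after randomisation, so the contrast is not to be read as pure effect modification by endovascular treatment; restriction removes the mixing of diagnoses and nothing more.

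The cost is one line of wording. Final diagnosis and both treatments are already collected (8.1.3). The comparison group shrinks and the interval widens a little: in the example above, the SE of the log ratio goes from 0.32 to 0.33, or from 0.24 to 0.26.
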